**To be completed by a member of the clinic staff**

- |                                                                                                          |   |                 |
|----------------------------------------------------------------------------------------------------------|---|-----------------|
| 7. FEV 1 pre-bronchodilator:_____                                                             | 0 | > 95% predicted |
|                                                                                                          | 1 | 95 - 90%        |
| FEV 1 predicted:_____                                                                         | 2 | 89 – 80%        |
|                                                                                                          | 3 | 79 – 70%        |
| FEV 1 % predicted:_____                                                                       | 4 | 69 – 60%        |
| (Record actual values on the dotted lines and score the FEV 1 % predicted in the next column) | 5 | 59 – 50%        |
|                                                                                                          | 6 | < 50% predicted |

FEV1 = forced expiratory volume in 1 second

© 2001 QOL Technologies LTD. ACQ-United Kingdom/English– Modified on 08 Sep 2010- Mapi Research Institute.

## 14.0 APPENDIX II: PATIENT GLOBAL IMPRESSION OF CHANGE (PGIC) SCALE

Since beginning of treatment (Day 1) in this study, how would you describe the change (if any) in ACTIVITY LIMITATIONS, SYMPTOMS, EMOTIONS and OVERALL QUALITY OF LIFE, related to your asthma? (Please tick ONE box).

- 1 = Very much improved
- 2 = Much improved
- 3 = Minimally improved
- 4 = No changes
- 5 = Minimally worse
- 6 = Much worse
- 7 = Very much worse

## **15.0 APPENDIX III: CLINICAL GLOBAL IMPRESSION OF CHANGE (CGIC) SCALE**

Since this patient has started the study treatment (Day 1) how would you describe the change (if any) in this patient's overall asthma symptoms and control compared to their asthma on Day 1. Please tick ONE box.

- 1 = Very much improved
- 2 = Much improved
- 3 = Minimally improved
- 4 = No changes
- 5 = Minimally worse
- 6 = Much worse
- 7 = Very much worse

## **16.0 APPENDIX IV: GLOBAL INITIATIVE FOR ASTHMA (2016) ASSESSMENT OF SEVERITY AND STEP THERAPY**

### **Assessing Asthma Severity**

Asthma severity is assessed retrospectively from the level of treatment required to control symptoms and exacerbations. It can be assessed once the patient has been on controller treatment for several months and, if appropriate, treatment step down has been attempted to find the patient's minimum effective level of treatment. Asthma severity is not a static feature and may change over months or years.

[figure not shown]
Asthma severity can be assessed when the patient has been on regular controller treatment for several months:

**Mild asthma** is asthma that is well controlled with Step 1 or Step 2 treatment, i.e. with as needed reliever medication alone, or with low-intensity controller treatment such as low dose inhaled corticosteroids (ICS), leukotriene receptor antagonists, or chromones.

**Moderate asthma** is asthma that is well controlled with Step 3 treatment e.g. low dose ICS/long-acting beta-2-agonists (LABA).

**Severe asthma** is asthma that requires Step 4 or 5 treatment, e.g. high-dose ICS/LABA, to prevent it from becoming 'uncontrolled', or asthma that remains 'uncontrolled' despite this treatment. While many patients with uncontrolled asthma may be difficult to treat due to inadequate or inappropriate treatment, or persistent problems with adherence or comorbidities such as chronic rhinosinusitis or obesity, the European Respiratory Society/American Thoracic Society Task Force on Severe Asthma considered that the definition of severe asthma should be reserved for patients with refractory asthma and those in whom response to treatment of comorbidities is incomplete.

**Step Therapy**

Abbreviations: ICS = inhaled corticosteroids; LABA = long-acting beta-2-agonists; LTRA = leukotriene receptor antagonists; Med = medium; OCS = oral corticosteroids; SABA = short-acting beta agonists.

Global Initiative for Asthma. Global Strategy for Asthma Management and Prevention, 2016. Available from: [www.ginasthma.org](http://www.ginasthma.org)

## 18.0 APPENDIX VI: PHARMACOKINETIC, INTERFERON-GAMMA, ANTI-DRUG ANTIBODY, AND BIOMARKER CYTOKINES COLLECTION TIME POINTS

Study Visit	Pharmacokinetic Sample Time Point (Serum)	Sample Time Point for ex vivo induced IFN- $\gamma$	Sample Time Point for ADA	Pharmacodynamic Sample Time point for Cytokines (Serum)
Day 1 ANB020/ Placebo Dosing	Pre-dose ( $\geq 5$ minutes)	Pre-dose ( $\geq 5$ minutes)	Pre-dose ( $\geq 5$ minutes)	Pre-dose ( $\geq 5$ minutes)
	0.50 hours ( $\pm 5$ minutes) post-start of infusion			
	EOI ( $\pm 3$ minutes)			
	EOI+3 hours ( $\pm 10$ minutes)			
	EOI+6 hours ( $\pm 10$ minutes)			
Day 2	24 hours ( $\pm 120$ minutes) post-start of infusion			24 hours ( $\pm 120$ minutes) post-start of infusion
Day 8	168 hours ( $\pm 120$ minutes) post-start of infusion		168 hours ( $\pm 120$ minutes) post-start of infusion	168 hours ( $\pm 120$ minutes) post-start of infusion
Day 22	504 hours ( $\pm 120$ minutes) post-start of infusion			504 hours ( $\pm 120$ minutes) post-start of infusion
Day 36	840 hours ( $\pm 120$ minutes) post-start of infusion		840 hours ( $\pm 120$ minutes) post-start of infusion	840 hours ( $\pm 120$ minutes) post-start of infusion
Day 64	1512 hours ( $\pm 120$ minutes) post-start of infusion			1512 hours ( $\pm 120$ minutes) post-start of infusion
Day 85			2016 hours ( $\pm 120$ minutes) post-start of infusion	
Day 106			2520 hours ( $\pm 120$ minutes) post-start of infusion	

Study Visit	Pharmacokinetic Sample Time Point (Serum)	Sample Time Point for ex vivo induced IFN-<math>\gamma</math>	Sample Time Point for ADA	Pharmacodynamic Sample Time point for Cytokines (Serum)
Day 127 EOS/ ET a		3024 hours ( $\pm$ 120 minutes) post-start of infusion	3024 hours ( $\pm$ 120 minutes) post-start of infusion	3024 hours ( $\pm$ 120 minutes) post-start of infusion

Abbreviation: ADA = anti-drug antibody, EOI = actual time of end of infusion, EOS = End of study, ET = early termination, IFN- $\gamma$  = interferon-gamma.

Time point details may shift beginning Day 36 depending on use of +/- 2-day window.

- a If the patient discontinues from study before Day 127 and returns to site for early termination (ET) visit, the samples for IFN- $\gamma$ , ADA, and cytokines will be collected at ET visit. A sample for PK analysis will also be collected if the ET visit occurs between Day 1 to Day 64. Duplicate samples will not be collected if the sample at ET visit would fall within another specified sample time/window.

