## 5.0 STUDY TREATMENTS

### 5.1 Treatments Administered

ANB020 is a humanized IgG1/kappa mAb and was selected from a panel of mouse mAb humanized by complementarity-determining region-grafting, optimized and matured via mammalian cell display and somatic hyper mutation using AnaptysBio's (SHM)-XEL™ system to achieve a desired functional inhibitory potency.

ANB020 will be administered to patients by IV infusion in polyvinyl chloride or polyolefin bags following dilution to a total volume of 100 mL with sterile normal saline (0.9% sodium chloride [NaCl]). Placebo will be administered by IV infusion as 100 mL sterile normal saline (0.9% NaCl). Infusions will be administered over 1 hour.

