**Table 5.1 Dosing Schedule**

Investigational product	Dosage form and strength	Manufacturer
ANB020	IV infusion: 300 mg/100 mL once on Day 1	Patheon

Abbreviation: IV = intravenous

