## **5.6 Selection and Timing of Dose for Each Patient**

Patients will receive a single dose of ANB020 or placebo administered under supervision at the study center. The infusion will be administered at the rate of 100 mL per hour via a Baxter infusion solutions set (FNC2110; prime volume 16 mL) or equivalent followed by a 16 mL IV saline flush, at the same infusion rate, to ensure that no residual drug remains in the infusion line. No in-line filter is to be used. Infusions will be administered over 1 hour. The ANB020 or placebo infusion may be slowed or interrupted for patients experiencing infusion-related AEs.

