[figure not shown]

Version Number: 1.0 Version Date: 18Dec2018

AnaptysBio Inc. PROTOCOL ANB020-004 Page 8 of 19

Figure 14 4 2 1 Waterfall plot: Change from Baseline in Peripheral Eosinophil Count on Day 22 – Pharmacodynamic Analysis Set

Programming Note: This is graph is only for representation purpose Y axis should have the % change from baseline, X-axis should have the treatments

Figure 14 4 2 2 Waterfall plot: Change from Baseline in Peripheral Eosinophil Count on Day 127/ET – Pharmacodynamic Analysis Set

Programming note: The abive layout should be followed

Version Number: 1.0 Version Date: 18Dec2018

[figure not shown]

AnaptysBio Inc. PROTOCOL ANB020-004 Page 9 of 19

Figure 14 4 1 1

Mean (±SD) Serum Concentration Time Profile of ANB020 for IV infusion – Safety Analysis Set

Linear Scale

End of infusion (EOI) was approximately 1 hour after the start of infusion and is plotted as 1 hour

SD = standard deviation

<Note: Plot is for example. Actual plot will have x- and y-axes and time points modified according to actual study data.>

Figure 14 4 1 1 (Cont'd)
Mean (±SD) Serum Concentration Time Profile of ANB020 for IV infusion – Pharmacokinetic Analysis Set

[figure not shown]
Version Number: 1.0 Version Date: 18Dec2018

CONFIDENTIAL

AnaptysBio Inc. PROTOCOL ANB020-004 Page 10 of 19

Semi-logarithmic scale

End of infusion (EOI) was approximately 1 hour after the start of infusion and is plotted as 1 hour

SD = standard deviation

<Note: Plot is for example. Actual plot will have x- and y-axes and time points modified according to actual study data.>

Version Date: 18Dec2018

1.0

[figure not shown]
Version Number:

CONFIDENTIAL

AnaptysBio Inc. PROTOCOL ANB020-004 Page 11 of 19

Figure 14 4 1 2 Individual Serum Concentration Time Profile of ANB020 for IV infusion - Safety Analysis Set Patient 1 Linear Scale

<Programming Note: Present all the patients. A linear and semi-log plot will be prepared for each subject > <Note: Plot is for example. Actual plot will have x- and y-axes and time points modified according to actual study data.>

\\ieedc-vnasc01\biosdata\AnaptysBio\ANB020\CYA74392\Biostatistics\Documentation\SAP\Final\20181218 Document: Author:

Version Number: 1.0 Version Date: 18Dec2018

[figure not shown]
153

29 June 2020

AnaptysBio Inc. PROTOCOL ANB020-004 Page 12 of 19

 $Figure~14~4~1~2~(Cont'd)\\ Individual~Serum~Concentration~Time~Profile~of~ANB020~for~IV~infusion-Safety~Analysis~Set\\ Patient~1$

Semi-logarithmic scale

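### Protocol Appendix VI does not say whether the EOI PK sample falls before or after the line flush; read as bag-empty, it precedes delivery of about 16% of the dose and tends to shift tmax from about 1 h to about 4 h

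*Protocol*

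**What the plan says.** **Infusion and line.** Protocol section 5.1 has ANB020 given "following dilution to a total volume of 100 mL with sterile normal saline", and Table 5.1 gives the dose as "IV infusion: 300 mg/100 mL once on Day 1". Section 5.6 sets the rate ("The infusion will be administered at the rate of 100 mL per hour"), names an infusion set or equivalent ("prime volume 16 mL"), and says the infusion is "followed by a 16 mL IV saline flush, at the same infusion rate, to ensure that no residual drug remains in the infusion line". The same section adds: "Infusions will be administered over 1 hour".

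**Sampling.** Appendix VI places PK samples on Day 1 pre-dose, at 0.5 h after the start of infusion, at EOI (±3 minutes), at EOI+3 h and at EOI+6 h (±10 minutes each), and next at 24 h. Its abbreviation list has "EOI = actual time of end of infusion" and does not mention the flush.

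**Recording and display.** Section 5.10 sends infusion start and end times to the eCRF, without saying whether the flush counts and without a separate flush time. The SAP shell for Figure 14.4.1.1 carries the note "End of infusion (EOI) was approximately 1 hour after the start of infusion and is plotted as 1 hour".

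**Endpoints.** Protocol section 9.6.1 names Cmax and tmax and allows further parameters. SAP section 17.2.2 lists those two plus seven more. Parameters are calculated from actual elapsed sampling times (Protocol 9.6.1, SAP section 19).

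**The concern.** Section 5.6 itself recognises that drug is still in the tubing when the infusion finishes; that is the flush's stated purpose. Because the flush follows the infusion, a site taking the words at face value would mark EOI when the bag runs dry and draw the peak sample within 3 minutes. The last part of the dose would still be in the line, and the next sample would be 3 hours away.

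A site that counts the flush as part of the infusion would draw the sample at the real peak. Both sites comply with Appendix VI, and the eCRF entry does not show which reading was used. At stake are the two PK parameters the protocol names, in about 12 ANB020 patients (section 6.2.2) spread over 7 centers (SAP section 7.2). Using actual elapsed times does not help: it records when the sample was drawn, but the sample still precedes full delivery.

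**Working it through.** **Inputs from the documents.** Volume 100 mL, dose 300 mg (3 mg/mL), rate 100 mL/h, line volume 16 mL, flush 16 mL at 100 mL/h, EOI window ±3 min, next sample at EOI+3 h, terminal half-life about 14 to 17 days (Phase I single-dose part, Protocol section 2.1).

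**The plan's own figure.** 100 mL ÷ 100 mL/h = 60 min. This reproduces the stated 1 hour.

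**Flush against window.** 16 mL ÷ 100 mL/h = 9.6 min, longer than 3 min. A sample taken within 3 min of bag-empty cannot follow the end of the flush.

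**Undelivered drug at bag-empty + w minutes** = 16 − (100/60) × w mL, at 3 mg/mL. This assumes no mixing in the line and a flush that starts at once.

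| w (min) | mL | mg | % of dose |
|---|---|---|---|
| −3 | 21 | 63 | 21 |
| 0 | 16 | 48 | 16 |
| +3 | 11 | 33 | 11 |

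**Does line priming matter?** The documents do not say what fills the line at the start.
- Saline-primed: the bag empties at 60 min and the flush ends at 60 + 9.6 = 69.6 min.
- Drug-primed from the bag: the bag holds 84 mL at the start and empties at 84 ÷ 100 h = 50.4 min; the flush ends at 60 min.

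The clock times differ, but in both cases 16 mL of drug is in the line at bag-empty, and the modelled bag-empty sample reads 84% of the peak (79–89% across the window). What matters is bag-empty versus flush end.

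**One compartment, bag-empty EOI at 1.00 h, flush end at 1.16 h.** The EOI sample is at 84% of the peak. The EOI+3 h sample is drawn at 4.00 h, which is 2.84 h after full delivery:
- 14 days: exp(−ln 2 × 2.84/336) = 0.994
- 17 days: exp(−ln 2 × 2.84/408) = 0.995

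Observed Cmax is about 0.5% low, and tmax is 4.00 h instead of 1.16 h.

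**Two compartments, no assay noise.** The documents give no distribution phase, so its share and half-life are assumptions. Terminal half-life is 14 days; 17 days gives the same picture.

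| Fast share, fast half-life | EOI / peak | EOI+3 h / peak | Observed Cmax / peak | tmax (h) |
|---|---|---|---|---|
| 0.3, 72 h | 0.840 | 0.988 | 0.988 | 4.00 |
| 0.3, 24 h | 0.841 | 0.972 | 0.972 | 4.00 |
| 0.5, 24 h | 0.841 | 0.958 | 0.958 | 4.00 |
| 0.5, 12 h | 0.842 | 0.922 | 0.922 | 4.00 |
| 0.5, 6 h | 0.844 | 0.861 | 0.861 | 4.00 |
| 0.7, 6 h | 0.845 | 0.806 | 0.845 | 1.00 |
| 0.7, 3 h | 0.850 | 0.673 | 0.850 | 1.00 |

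With EOI at flush end, observed Cmax equals the peak in every row and tmax is 1.16 h.

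**Two compartments with assay noise.** Assumed V1 3 L, V2 2.5 L, Q 0.5–1 L/day, half-life 14–20 days and assay CV 5–10%, with 200,000 draws. Compared with sampling at flush end, mean observed Cmax is 3–5% lower. The share of patients whose tmax falls on the EOI sample drops from about 46–74% to about 1–11%.

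**The case against.** **The wording is open.** Appendix VI does not say bag-empty. Sampling details are deferred to a laboratory manual (Protocol section 7.3) that is not part of these documents and may settle the matter. With a drug-primed line, full delivery falls at exactly 60 min, which fits both the stated 1 hour and the SAP figure note. This stands, so it cannot be said that samples are taken early, only that the protocol permits it. Priming does not remove the ambiguity, however, because a bag-empty sample would then fall at 50.4 min with the same 16 mL outstanding.

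**A 16% dose deficit is not a 16% error in Cmax.** A reader might infer that it is. The EOI+3 h sample follows full delivery and mostly rescues Cmax. A loss of about 15–16% appears only under the fastest distribution assumed above.

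**tmax is only described.** It is summarised by n, minimum, median and maximum (Protocol 9.6.3, SAP section 6), with no test or decision attached. In the noisy model it is unstable even with correct timing, since only about 46–74% of patients peak at EOI. Both points are fair. They limit the consequence but do not remove a systematic shift of about 3 h.

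**Two further inferences do not hold.**
- It is tempting to call 116 mL at 100 mL/h a contradiction of the 1-hour infusion. If the flush is separate from the infusion, 100 mL at 100 mL/h is 60 min. If it is included, a drug-primed line also finishes at 60 min.
- It is also tempting to extend the problem to Vss through the infusion-duration term in SAP section 19. A 9.6-min change moves half the duration by 4.8 min, against a mean residence time of about 14 ÷ ln 2 ≈ 20 days: under 0.02%. No material effect on AUC, clearance or half-life was shown either.

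**Conclusion.** The concern holds conditionally. The protocol leaves EOI undefined relative to the flush, and its more natural reading puts the peak sample before delivery of 48 mg, 16% of the dose (11–21% across the window). On that reading the EOI sample reads about 84% of the peak. The documents do not support saying that Cmax and tmax are misstated in this trial, since how sites applied EOI is not stated.

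If EOI is taken as bag-empty, the likely loss in Cmax is small: about 0.5% with one compartment and about 3–5% in the noisy two-compartment models. The main effect is a tmax near 4 h instead of near 1 h, plus avoidable spread if sites differ. The volumes, rate, window and terminal half-life come from the documents. Distribution parameters, assay CV, unmixed flow in the line and an immediate flush are assumptions. Cmax and tmax are the only PK parameters the protocol names, but not the only ones the SAP analyses.

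**What to change.** In Appendix VI, define EOI for PK sampling as the actual time the saline flush ends, and time the EOI, EOI+3 h and EOI+6 h samples from it. Add a flush-end time to the eCRF alongside the infusion times in section 5.10. Reconcile Protocol sections 5.6 and 5.10, Appendix VI and the SAP Figure 14.4.1.1 note on whether the end of infusion includes the flush. This concerns the sampling clock only; how the infusion is given is for the sponsor to state.

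Do not remove EOI samples already taken. Without a recorded flush-end time, the early ones cannot be identified, and dropping them would itself push tmax to about 4 h.

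The cost is a wording change and one extra eCRF time field, with no extra sample.

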## 19.0 APPENDIX 7: SUMMARY OF CHANGES

### **Protocol ANB020-004: Amendment 3, 16 February, 2018**

#### **Replaces: Amendment 2, 04 January, 2018**

1. Inclusion Criteria Updated:  
Description of Change: Lowered required blood eosinophil count from  $\geq 400$  to  $\geq 300$  cells/ $\mu$ L.  
Purpose for Change: To enable enrollment of severe eosinophilic patients with levels of  $\geq 300$  cells/ $\mu$ L.
  
2. Section 5.4 (Method of Assigning Patients to Treatment Group):  
Description of Change: Removed specific details on randomization responsibilities.  
Purpose for Change: Instructed site to reference study manuals for complete information/instruction.
  
3. Section 5.7.2 (Unblinding):  
Description of Change: Removed specific details on unblinding language.  
Purpose for Change: Site staff to reference study manuals for detailed processes.

### **Protocol ANB020-004: Amendment 2, 04 January, 2018**

#### **Replaces: Amendment 1, 08 May 2017**

1. Entire Document:
  - a. Description of Change: Updated CRO name from QuintilesIMS to IQVIA.  
Purpose for Change: Vendor name change.
  - b. Description of Change: General grammatical and typographical corrections.  
Purpose for Change: Correcting errors.

2. Synopsis- Study Center:  
Description of Change: Updated number of study centers.  
Purpose for Change: Increase number of sites participating in protocol.
  
3. Section 2.1- (Background Information) and Section 4.2 (Discussion of Study Design):  
Description of Change: Updated background to include MAD information.  
Purpose for Change: Updated to reflect completion of MAD study as reflected in current IB.
  
4. Section 4.1 (Summary of Study Design):  
Description of Change: Clarification of informed consent window.  
Purpose for Change: Remove “-14-day” window restriction to allow consent prior to screening visit.
  
5. Section 4.3.1 (Inclusion Criteria):
  - a. Description of Change: Increased body mass index.  
Purpose for Change: Increased to reflect BMI of patient population.
  
  - b. Description of Change: Clarified WOCBP language.  
Purpose for Change: Clarified to address Investigator questions.
  
  - c. Description of Change: Inclusion Systemic corticosteroids dosage criteria, removal of stable dose requirement.  
Purpose for Change: Removed stable dosage requirement to correspond with SOC treatment prior to beginning study treatment.
  
6. Section 4.3.2 (Exclusion Criteria)
  - a. Description of Change: Removed exclusion: “Participation in any interventional study for the treatment of asthma in the 6 months before screening.”  
Purpose for Change: Removed, covered in exclusion criteria “3 months or 5 half-lives before screening.”
  
  - b. Description of Change: Removed exclusion for use of beta blockers, angiotensin-converting enzyme inhibitors, angiotensin-receptor blockers, or calcium channel blockers.  
Purpose for Change: Use of beta blockers, etc. will not affect safety of participants and will allow SOC treatment to continue.
  
  - c. Description of Change: Inclusion amended to allow admission of controlled cardiovascular disease (controlled ischemic cardiovascular disease).

Purpose for Change: Allow inclusion of typical patient population.

7. Section 4.3.4 (Patient Restrictions):

Description of Change: Clarified language regarding partners of male patients and clarified “Highly Effective Methods of Contraception” language to reflect local naming conventions.

Purpose for Change: Clarified requirements for contraception.

8. Section 4.3.5 (Patient Withdrawal):

Description of Change: Added notification instructions for staff.

Purpose for Change: Provide instruction to site regarding notification procedures.

9. Section 5.8.1 (Excluded Medications):

Description of Change: Removed restricted medications per inclusion/exclusion updates.

Purpose for Change: Updates correspond to revised inclusion/exclusion criteria.

10. Section 6.1.2 (Spirometry):

Description of Change: Addition of pre-bronchodilator Spirometry readings at each clinic visit.

Purpose for Change: Additional Spirometry reading collected to ensure stable collection of data.

11. Section 6.2.6 (Timing of Procedures):

a. Description of Change: Corrected order of blood draw.

Purpose for Change: Updated to reflect laboratory instruction guidelines.

b. Description of Change: Removed repetitive Quality of Life instruction.

Purpose for Change: Removed repetitive instruction that is covered in bullet point #3 (study scales/questionnaire forms).

12. Section 18 (Appendix VI - IFN- $\gamma$  collection time points):

Description of Change: Removed select IFN- $\gamma$  blood draws.

Purpose for Change: Additional blood draws unnecessary per data collected in previous trials.

13. Table 4.1 (Schedule of Events):

Description of Change: Corrected footnotes to reflect Amendment 2 changes.

Purpose for Change: Updated to reflect necessary changes in procedure requirements.

